9.10 Study Discontinuation

The following data will be recorded as available from any enrolled subjects who withdrew consent during the Registry:

- SAEs/AEs - Method of treatment, severity, etc.
- Concomitant medications including dosages
- Reason for withdrawal

10. COMPLAINT AND SAFETY REPORTING

Principal Investigators were taught to use FDA 3500A MedWatch (Appendix C) and were taught to fill those out during the investigator meeting, for relevant SAEs and also for medical device complaints. This registry's primary safety objective is to collect localization-related safety events in patients undergoing wedgectomy.

The Medical Device Reporting (MDR) regulation (21 CFR 803) contains mandatory requirements for device user facilities (including hospitals, surgical facilities and other) to report certain device-related serious adverse events and product problems to the FDA. These are described in further detail below.

- User facilities must report a suspected medical device-related death to both the FDA and the manufacturer within 10 days.
- User facilities must also report a medical device-related serious injury to the manufacturer (Veran Medical Technologies, address below).
- In addition, each IRB and institution may have its own policies regarding the content, format, and timing for the reporting of SAE information.

Each investigator is responsible for fulfilling these duties. Please report device serious adverse events to Veran as noted below on form 3500A (Appendix C):

Email: [contact]

Email: [contact]

10.1 Complaint Reporting

A device deficiency is an inadequacy of a medical device related to its identity (e.g. labeling), quality, durability, reliability, safety or performance, such as malfunction. It can also include a broken needle. It is important to Veran Medical Technologies to be aware of and remedy any device deficiencies. Please submit complaints or product problems to Veran Medical Technologies, using form 3500A (Appendix C).

User facilities are not required to report a device malfunction to the FDA. They can voluntarily inform the Agency of such product problems through MedWatch, using form 3500A (Appendix C).

Please report device deficiencies to Veran as noted below on form 3500A:

Email: [contact]

Email: [contact]

10.2 Safety Reporting

All SAEs and device deficiencies related to the Veran system or its instruments are also to be reported directly to Veran as follows: (please send to **vSupport**, and Cc: the **PLOTS** email)

Email: [contact]

Email: [contact]

For any FDA-reportable event, please also forward to the following for awareness:

Contact: [name]
[contact]
Email: [contact]

Safety events from the localization procedure only will be collected in the registry (please refer to Appendix B for all data elements collected in Registry).

This study is being conducted under 21 CFR part 50¹ (<https://www.ecfr.gov/cgi-bin/textidx?SID=244dabc113521b0a851a5db147554fdd&mc=true&node=pt21.1.50&rgn=div5>) using a 510(k)-cleared device system. The exemption in 21 CFR 812.2(c)(2) applies to this study, where the device is substantially equivalent to its predicate, and the device is being used in accordance with its labeling.

Study sites are likewise responsible to report adverse events and complications to their IRBs according to institutional requirements.

10.3 Adverse Events – Data Collection for Localization Events

An adverse event (AE) is any untoward medical occurrence, unintended disease or injury, or untoward clinical signs (including abnormal laboratory findings) in subjects, users or other persons, whether or not related to the investigational medical device. Note: Pre-existing conditions are not considered to be adverse events unless there is a change in the nature or severity of the condition.

We will collect data on the localization adverse event through subject discharge from hospital. Principal Investigators were taught to use FDA 3500A MedWatch (Appendix C) and were taught to fill those out during the investigator meeting, for relevant SAEs and also for medical device complaints. This registry's primary safety objective is to collect localization-related safety events in patients undergoing localization prior to wedgeectomy.

The Medical Device Reporting (MDR) regulation (21 CFR 803) contains mandatory requirements for device user facilities (including hospitals, surgical facilities and other) to report certain device-related serious adverse events and product problems to the FDA. These are described in the forms in Appendix C, and the FDA's Guidance for User Facilities.

- User facilities must report a suspected medical device-related death to both the FDA and the manufacturer within 10 days.
- User facilities must also report a medical device-related serious injury to the manufacturer (Veran Medical Technologies, address below).
- In addition, each IRB and institution may have its own policies regarding the content, format, and timing for the reporting of safety information.

¹ The Electronic Code of Federal Regulations (www.ecfr.gov) - <https://www.ecfr.gov/cgi-bin/textidx?SID=244dabc113521b0a851a5db147554fdd&mc=true&node=pt21.1.50&rgn=div5> accessed 4/16/2019.

Each investigator or delegate is responsible for fulfilling these duties.
Please report device serious adverse events to Veran as noted below on form 3500A
(Appendix C).

Please scan and send completed forms to:
Email: [contact]
Email: [contact]

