--	---

	PHI and privacy. All data collected into the study database will be de-identified at the site level.
STUDY PROCEDURES	
Subjects are treated for lung resection according to the treatment devised by their clinician.
 
Part of the technical procedure registry trains thoracic surgeons on the various available tools and techniques in intraoperative localization, using both didactic review, best practices, case review, and a cadaver lab.
 
The following represents the typical standard of care for this procedure. The registry study is nested within the standard lung resection operation, and study procedures on data collection are described within the context of these procedures for clarity of identification:
 
Following nodule identification and referral, subjects are typically evaluated per the subject inclusion/exclusion criteria. Review of the subject's CT/PET scan demonstrate a PPN that is between 0.4 cm and 3.2 cm in its longest dimension. All subjects will sign and date an Informed Consent Form (ICF) before enrollment (Baseline Visit).
 
Subjects will undergo a chest CT scan on the day of surgery, verifying the longest dimension of the nodule (data collected). The subject is put under general anesthesia. The SPiN Percutaneous nodule localization procedure is performed intraoperatively, using dye and/or other localization techniques. A surgical resection (wedge, segmentectomy etc.) will follow, according to PI's judgment. Subjects are generally hospitalized between 2-5 days following this procedure and discharged. Following discharge, subjects typically follow a schedule of multiple clinic visits, as determined by their healthcare team. Subject participation in the localization registry will end following hospital discharge.

ESTIMATED DURATION OF STUDY	The Registry is anticipated to take 24 months to complete.

STUDY POPULATION	
The target subject population includes adult subjects (18 years-85 years), with PPNs. In the judgment of the thoracic surgeon, localization for resection is warranted via a percutaneous localization approach. The establishment of malignancy is not necessary for PPN removal.
 
Data will be collected from study subjects having a PPN between 0.4 cm and 3.2 cm in greatest dimension, that are accessible to percutaneous localization, who consent to and undergo intraoperative dye/wire localization procedure followed by surgical lung resection.

-------------------------	--

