3. RATIONALE

Veran Medical Technologies, Inc. is seeking to characterize the efficient localization and successful removal of PPNs aided by the technique of percutaneous localization within the operating room. This falls within the current practice for these subjects. However, the characterization and comparison of various localization techniques has not been reported prospectively in a large, multicenter approach.

To realize this opportunity, further localization methodologies must be developed. Percutaneous nodule localization involves various factors. Nodular size and location (near the pleura) can both introduce challenges for unequivocal localization and complete removal. PPNs can be difficult to locate and access in order to mark them. It can be difficult to find the marked nodules, depending upon the location and how well the localization technique worked during the resection surgery. This registry will collect data regarding different techniques used by thoracic surgeons using a choice of localization materials (dye, hookwire etc.) and with electromagnetic navigation guidance using a transthoracic approach. Evidence from a multicenter, prospective registry trial on localization procedures will allow us to understand the best practices in the localization of PPNs that also minimizes risks in subjects who are typically older, have comorbid lung disease, poor pre-surgical lung function and may have early stage lung cancer.

[figure not shown]
Further, the study will allow us to describe the use of VERAN SPiN Thoracic Navigation System™ and percutaneous lung localization tools in a real-world thoracic surgery practice, including duration of localization procedure, duration of the resection procedure, and other data elements.

TABLE 1 – SCHEDULE OF EVENTS

Procedures/Data Collection	Baseline Visit	Day 0 Surgery Localization Procedure
Nodule is correct size and suitable for percutaneous localization during surgical resection procedure.	X	X
Subject meets Inclusion/Exclusion criteria review.	X	
Subject is able and willing, and signs consent form.	X	
Pregnancy test- urine or serum, for females of child-bearing potential.	X	X
Socio-demographic information.	X	
Pulmonary function test results	X	
Brief Medical History, including previous cancer diagnoses, smoking, and treatment history.	X	
Nodule hx, dx, characteristics if known.	X	
Recent (0-15 days) CT scan available, or schedule CT scan to be used on day of surgery, prior to procedure.	X	X

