9. RESEARCH METHODS AND DATA COLLECTION

In this study, the “lung resection and after care protocol” is determined by each investigator’s current practice, with an outline provided in the registry to explain the context for the type of data collection performed in this patient population. The medical device is being marketed for and used within its intended use.

Localization methods and outcomes, and data related to the nodules, diagnosis, and the setting of the planned clinical intervention of nodule removal will be recorded. Data will be collected according to descriptions below, Table 1 and Figure 1.

Collected data include brief medical history, smoking history, demographic characteristics, radiographic characteristics, procedural characteristics, crossover to other procedures, and adverse events, as follows:

- *Radiographic Characteristics:*

The location of the target nodule (side, lobe and segment, i.e. right upper lobe anterior segment, etc.) will be determined and recorded. The radiographic information collected from CT will include size of the nodule (longest axis), distance from a visible bronchus, and distance from the pleural surface perpendicular to the nodule.

- *Procedural Characteristics:*

Collected procedural information will include the distance of target from pleura nodule statistics (volume, RESIST diameter, maximum, minimum, and effective diameter), and target motion. The duration of the localization procedure will also be recorded.

- *Crossover to Other Procedures:*

All procedures performed to aid in the surgical management of patients – will be noted. Wedge resection, segmentectomy, and lobectomy. The type of initial surgery planned, and the eventual surgery done, will both be collected.

- *Adverse Events:*
All device and/or procedure related adverse events will be recorded for the study localization procedure. Events will be collected from the initiation of the localization procedure to the start of the wedge resection procedure. Study sites will report localization-related adverse events and complications to their IRBs according to institutional requirements. These will be recorded.

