9.3 Subject Enrolment and Informed Consent

Patients presenting to their physician in need of assessment or removal of peripheral pulmonary nodule(s), and who meet study inclusion/exclusion criteria, will be invited to participate. Patient enrolment will follow each participating institution's standard of care. Subjects will be approached to obtain informed consent prior to any study-specific procedure. Informed consent will take place in a private environment (e.g. patient exam room), free from distractions. The PI or study team member will approach the subject at their clinic appointment and will explain the study to qualified subjects prior to obtaining consent. All individuals who obtain consent (PI, Sub-investigators, and study coordinators) must have received GCP informed consent training within the past 2 years. Interviews to obtain consent will not follow any stressful situation (e.g. patient being informed he/she may have cancer) and will not be conducted if the patient has received any mind-altering medications or anesthesia. Patients will be assessed for their capacity to consent by the ability to show comprehension of the procedure, ask appropriate questions, and appear properly oriented.

The PI will confirm subject eligibility. Patients who sign the informed consent form will be considered enrolled. A signed copy of all consents and the HIPAA authorization document will also be given to consenting subjects.

Patients who complete the localization procedure will be included within the analysis population. Reasons for study withdrawal will be recorded. Each patient's participation in this study is approximately 6 weeks baseline through subject's discharge from hospital following lung surgery.

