9.9 Nodule Localization

The bronchoscope (Olympus MP-160 or BF-190) will be introduced into the airway. A Veran tip tracked instrument will then be introduced into the working channel of the bronchoscope and utilizing standard Veran System navigation-matching protocols, the main and secondary carinas are identified using the tip tracked instrument to confirm that the Veran System is properly matched to the airway defined by accurate matching of the main and secondary carina. This allows the system to align the CT with the patient's current position.

Following registration, a sterile field is created on the chest wall as identified by the Spin Perc planning software and the area is prepped and draped. A tip tracked needle, such as one of the Veran localization needles or the Veran tip tracked Spin Perc needle introducer, is selected. The surgeon advances the needle trans thoracically into the nodule, under Veran EMN guidance, to the nodule. The nodule is localized percutaneously by marking with dye using an assortment of tools designed for this purpose (Section 5.1), adding microcoils or fiducials, etc.

Data Collected: patient position, registration, volume of dye, type of dye, use of microcoils or fiducials.

The surgeon then continues to wedge resection, and the registry portion of the procedure is completed.

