10.5 Adverse Event Outcome

The outcome of AEs will be recorded as follows:

- *Resolved*: The event is considered fully resolved.
- *Continuing*: At study exit the event is considered ongoing.

Note: Any unresolved AE ongoing past study exit will be monitored by the physician per institutional standard of care.

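### Adverse-event data have conflicting end points: section 10.3 runs to hospital discharge, section 9 stops when wedge resection begins, and Table 1 has no adverse-event entry after Day 0

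*Combined protocol and SAP*

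**What the plan says.** Two sections carry adverse-event data beyond the operating day. Section 10.3 states: "We will collect data on the localization adverse event through subject discharge from hospital". Section 10.5 offers two outcome codes, resolved and continuing, and defines the second as "At study exit the event is considered ongoing". Study exit comes after discharge. The synopsis (Study Procedures) says "Subject participation in the localization registry will end following hospital discharge", and section 9.3 (Subject Enrolment and Informed Consent) runs participation from baseline to "discharge from hospital following lung surgery". The synopsis also describes the usual stay: "Subjects are generally hospitalized between 2-5 days following this procedure and discharged".

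Other places stop earlier. Section 9 makes its own descriptions and Table 1 the basis for data collection, and under Adverse Events says: "Events will be collected from the initiation of the localization procedure to the start of the wedge resection procedure". Section 9.3 (Safety Objective) ends the localization period at the last needle withdrawal and asks for events that develop during localization. Table 1 has two time columns, Baseline and "Day 0 Surgery Localization Procedure", and its row for AEs and SAEs is marked in those two. Section 9.9 closes with: "The surgeon then continues to wedge resection, and the registry portion of the procedure is completed".

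**The concern.** The safety objective in section 9.3 is the incidence and severity of localization-related AEs and SAEs, and section 11.2.1 promises to list and summarize them. Several of the protocol's own classifications depend on what happens after the needle is out. A site that follows section 9 and Table 1 could close the adverse-event record on Day 0 and believe itself compliant. A site that follows section 10.3 would keep it open to discharge. With about five sites, pooled safety summaries could then mix records closed at different times, and some seriousness ratings and outcomes would reflect only what was known on the operating day.

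**Working it through.** No arithmetic applies. The plan states no figure that depends on this window, and section 11.1 says that no formal sample size estimation was made. The check sets the stated end points side by side.

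**1. Stated end points**

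| Place | What it governs | End point |
|---|---|---|
| 9.3 Safety Objective | Localization period | Last needle withdrawal |
| 9, Adverse Events | Collection of events | Wedge resection begins |
| Table 1, AE/SAE row | Scheduled recording | Day 0 |
| 10.3 | Data on the localization event | Hospital discharge |
| 10.5 | Outcome code | Study exit |
| Synopsis; 9.3 Subject Enrolment | Participation | At or after discharge |

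**2. Can they be read together?** Partly. If sections 9 and 9.3 define when an event must begin in order to count, and 10.3 and 10.5 define how long a counted event is followed, most of the conflict goes away. No section says this. Section 9 is written as a rule about collecting events, not about their onset. Even on this reading three things remain:
- Section 9 and section 9.3 (Safety Objective) stop at different moments, resection start and needle withdrawal.
- Table 1 has no time point at which the follow-up in 10.3 and 10.5 is done.
- It is not stated whether a localization-related event first detected after resection has started counts towards the safety objective.

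**3. What depends on information after Day 0?**
- Section 10.3.1: prolonged hospitalization and permanent impairment generally cannot be judged on the operating day.
- Section 10.6: significant hemorrhage is bleeding seen at the procedure that leads to a higher level of care, transfusion or a separate intervention. The onset is on Day 0, but the consequence may come later.
- Section 10.5: an event still present at the end of Day 0 can be coded only as continuing unless the record is reopened.

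**4. Direction.** If a Day 0 record is not updated, later consequences are missed. The error therefore runs towards too few serious events and too many outcomes left as continuing.

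**5. Extent.** The ambiguity covers every planned subject (70-100) and the usual 2-5 inpatient days. That is the exposure to the problem, not a count of misclassified events. Such a count would need a localization event rate and the share of sites closing records early, and the documents give neither.

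**6. Limits of the check.** The Table 2 flow diagram and Figure 1 were not available, only the Table 2 footnotes. Section 10.2 refers to Appendix B for the registry's data elements, but Appendix B is titled as the CT scan appendix. What the case report form captures at discharge therefore cannot be confirmed either way.

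**The case against.** The strongest reply is that collection to discharge is already required. Section 10.3 is an instruction, participation runs to discharge, and the synopsis (Study Design) says that registry data come from the medical record before, during and after the procedure. Table 1 is plainly not the full list of data items: it has no row for pathology margins, localization time or resection type, all required elsewhere. The Table 2 footnotes record hospital days and discharge day without any Table 1 column. Section 12.1 allows eCRF changes under an audit trail, so nothing locks on Day 0.

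Most of this stands, and it rules out four stronger readings that a reader might infer:
- *That in-hospital follow-up is never collected.* Absence from Table 1 does not show this, and 10.3 says otherwise.
- *That section 9.9 closes the registry at resection.* It closes only the registry part of the procedure, meaning the intraoperative steps.
- *That a later death would remain a non-serious event.* Sections 10, 10.2 and 10.3 require reporting of device-related SAEs and suspected device-related deaths, with no Day 0 cut-off. Some seriousness criteria, such as life-threatening injury, can also be evident during surgery.
- *That the number affected can be projected from the 21% pneumothorax rate in section 7.* That rate comes from a 24-subject biopsy pilot, not from localization followed at once by resection. The projection would also require every site to disregard 10.3.

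The reply does not remove the contradiction in section 9. This is not mere silence in a table: section 9 names Table 1 as a basis for collection and states an earlier stop. Hospital days and discharge day do not record an event's status, seriousness or resolution, and the device-reporting route is limited to device-related events.

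**Conclusion.** The conflict is real and should be corrected. The protocol gives several end points for adverse-event data and does not say which of them govern onset and which govern follow-up. Follow-up to discharge is instructed by 10.3, contradicted by section 9 and not scheduled in Table 1. The consequence is possible variation between sites and possible under-recording of seriousness and outcome for events not updated after Day 0. Its size cannot be estimated from the documents.

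The conclusion assumes that Table 1 reads as it appears, with the AE/SAE row marked at Baseline and Day 0 only, and that neither the Table 2 diagram nor the case report form already sets a discharge entry. If either does, the scheduling gap closes, but the wording of sections 9, 9.3 and 10.3 would still need to be reconciled.

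**What to change.** - State two windows separately: the onset window (when an event must begin to count as a localization event) and the follow-up window (how long its status, seriousness and outcome are updated). Reconcile section 9, section 9.3 (Safety Objective) and section 10.3 to match.
- Say whether a localization-related event first detected after resection has started is counted in the safety objective.
- Add a discharge/study-exit column to Table 1, marked for AE/SAE status, seriousness, outcome and resolution date, completed from the chart.
- In section 9.9, at most clarify that the closing sentence refers to the intraoperative steps and does not end adverse-event follow-up.

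The cost is a protocol wording change, one table column and one chart-based eCRF page. Discharge day is already recorded, so no visit or procedure is added.
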